6.3 Planned Duration of Subject's Participation in the Trial

Expected duration of trial participation for each subject is up to 85 days.

6.4 Premature Termination or Suspension of Trial or Investigational Site

6.4.1 Criteria for Premature Termination or Suspension of the Trial

The trial will be completed as planned unless one or more of the following criteria that require temporary suspension or early termination of the trial are satisfied:

- New information or other evaluation regarding the safety or efficacy of the trial vaccine that indicates a change in the known risk/benefit profile, such that the risk/benefit is no longer acceptable for subjects participating in the trial.
- Significant deviation from GCP that compromises the ability to achieve the primary trial objectives or compromises subject safety.
- The sponsor decides to terminate or suspend the trial.

6.4.2 Criteria for Premature Termination or Suspension of the Investigational Site

A trial site may be terminated prematurely or suspended if the site (including the investigator) is found in significant deviation from GCP, the trial protocol, or contractual agreement, is unable to ensure adequate performance of the trial, or as otherwise permitted by the contractual agreement.

6.4.3 Procedures for Premature Termination or Suspension of the Trial or the Participation of the Investigational Site

In the event that the sponsor, an institutional review board (IRB) or regulatory authority elects to terminate or suspend the trial or the participation of an investigational site, a trial-specific procedure for early termination or suspension will be provided by the sponsor; the procedure will be followed by applicable investigational sites during the course of termination or trial suspension.

7.0 SELECTION AND DISCONTINUATION/WITHDRAWAL OF SUBJECTS

All entry criteria, including test results, need to be confirmed prior to trial vaccine administration.

7.1 Inclusion Criteria

Subject eligibility is determined according to the following criteria:

1. Male or female subjects aged 18 to 49 years, inclusive.
2. Individuals who are in good health at the time of entry into the trial as determined by medical history, physical examination (including vital signs) and clinical judgment of the investigator.
3. The individual signs and dates a written, informed consent form and any required privacy authorization prior to the initiation of any trial procedures after the nature of the trial has been explained according to regulatory requirements.
4. Individuals willing and able to comply with trial procedures and are available for the duration of follow-up.

7.2 Exclusion Criteria

Any subject who meets any of the following criteria will not qualify for entry into the trial:

1. Behavioral or cognitive impairment or psychiatric disease that, in the opinion of the investigator, may interfere with the subject's ability to participate in the trial.
2. History of drug abuse (defined as any illicit drug use) or a history of alcohol abuse within 2 years prior to Visit 1.
3. Female subjects who are pregnant or breastfeeding.
4. Female subjects of child-bearing potential who are sexually active with men and have not used any of the acceptable contraceptive methods for at least 2 months prior to trial entry.
 - a) Of childbearing potential is defined as status post-onset of menarche and not meeting any of the following conditions: menopausal for at least 2 years, status after bilateral tubal ligation for at least 1 year, status after bilateral oophorectomy, or status after hysterectomy.
 - b) Acceptable birth control methods are defined as one or more of the following:
 - I. Hormonal contraceptive (such as oral, injection, transdermal patch, implant, cervical ring).
 - II. Double barrier methods (e.g., condom and cervical cap with spermicide or diaphragm with spermicide) every time during intercourse.
 - III. Intrauterine device.

CONFIDENTIAL

IV. Monogamous relationship with vasectomized partner. The partner must have been vasectomized for at least six months prior to the subjects' trial enrollment.

5. Female subjects of childbearing potential who are sexually active and refuse to use an acceptable contraceptive method as outlined in the protocol, from the time of consent throughout the trial period for 6 months after the date of trial vaccine administration.
6. Female subjects who plan to get pregnant or to donate ova before consent, during the trial period for 6 months after the date of trial vaccine administration.
7. Any positive or indeterminate pregnancy test (Section 9.1.10).
8. Chronic use of oral corticosteroids (equivalent to 20 mg/day prednisolone for ≥ 12 weeks / ≥ 2 mg/kg body weight /day for ≥ 2 weeks) within 60 days prior to Visit 1 (use of inhaled, intranasal, or topical corticosteroids is allowed).
9. Use of parenteral corticosteroids (equivalent to 20 mg/day prednisolone for ≥ 12 weeks / ≥ 2 mg/kg body weight /day for ≥ 2 weeks. Use of inhaled, intranasal or topical corticosteroid is allowed) within 60 days prior to Visit 1.
10. Receipt of immunostimulants within 60 days prior to Visit 1.
11. Receipt of parenteral, epidural or intra-articular immunoglobulin (Ig) preparations, blood products, and/or plasma derivatives within 90 days prior to Visit 1 or planned during the full duration of the trial.
12. Receipt of immunosuppressive therapy within 6 months prior to Visit 1.
13. Known hypersensitivity or allergy to any of the trial vaccine components (including excipients).
14. Any clinically significant active infection (as assessed by the investigator) or temperature $\geq 38.0^{\circ}\text{C}$ (100.4°F), regardless of method used, within 3 days prior to intended trial vaccine administration.
15. Any serious chronic or progressive disease according to the judgment of the investigator (e.g., cardiac, neurological, renal, or hepatic disease).
16. History of any illness, that, in the opinion of the investigator, might interfere with the results of the trial or pose additional risk to the subjects due to participation in the trial.
17. Abnormalities of splenic or thymic function.
18. Known or suspected impairment/alteration of immune function.
19. Known bleeding diathesis, or any condition that may be associated with a prolonged bleeding time.
20. Receipt or scheduled receipt of any approved or authorized vaccines within 14 days (all non-live vaccines) or 28 days (for live vaccines) before or after trial vaccine administration.

21. Previous exposure to an experimental norovirus vaccine.
22. Participation in any clinical trial with another investigational product 30 days prior to first trial visit or intention to participate in another clinical trial at any time during the conduct of this trial.
23. Seropositive for human immunodeficiency virus.
24. Hepatitis B or C infection.
25. Known or suspected impairment/alteration of immune function, including history of any autoimmune disease or neuro-inflammatory disease.
26. Subject or subject's first-degree relatives are involved in the trial conduct.

There may be instances when individuals meet all entry criteria except one that relates to transient clinical circumstances (e.g., body temperature elevation or recent use of excluded medication[s] or vaccine[s]). Under these circumstances, eligibility for trial enrollment may be considered if the appropriate window for delay has passed, inclusion/exclusion criteria have been rechecked, and if the subject is confirmed to be eligible (Section 7.3).

7.3 Criteria for Delay of Trial Vaccine Administration and/or Blood Sampling

After enrollment, subjects may encounter clinical circumstances that warrant a delay in the administration of the trial vaccine. These situations are listed below. In the event that a subject meets a criterion for delay of trial vaccine administration, the subject may receive the trial vaccine once the window for delay has passed as long as the subject is otherwise eligible for trial participation:

- Subjects with a clinically significant active infection (as assessed by the investigator).
- Subjects with a body temperature $\geq 38.0^{\circ}\text{C}$ (100.4°F), within 3 days of planned trial vaccine administration.
- Subjects who received any approved or authorized vaccines within 14 days (all non-live vaccines) or 28 days (for live vaccines) prior to planned trial vaccine administration or blood sampling.
- Subjects who have used antipyretics and/or analgesic medications within 24 hours prior to trial vaccine administration. Trial vaccine administration should be delayed to allow for a full 24 hours to have passed between having used antipyretics and/or analgesic medications and trial vaccine administration.

7.4 Criteria for Early Termination of a Subject's Trial Participation

Under some circumstances, a subject's trial participation may be terminated early. This means that no further trial procedures (including data collection) will be performed on that subject beyond the specific date of early termination of trial participation. The primary reason for early

termination of the subject's trial participation should be documented using the following categories:

1. **Adverse Event:** The subject has experienced an AE (irrespective of being related/unrelated to the trial vaccine or trial-related procedures) that requires early termination because continued participation imposes an unacceptable risk to the subject's health and/or the subject is unwilling to continue participation because of the AE. The primary reason for early termination of trial participation in this case will be withdrawal due to AE and not withdrawal of consent, (see below).
2. **Lost to follow-up:** The subject did not return to the clinic and at least three documented attempts to contact the subject were unsuccessful.
3. **Withdrawal of consent:** The subject wishes to withdraw from the trial. The primary reason for early termination will be withdrawal of consent if withdrawal from participation is due to a non-medical reason (i.e., reason other than AE). While the subject has no obligation to provide a reason for withdrawing consent, attempts should be made to determine the underlying reason for the withdrawal and, where possible, the primary underlying reason should be documented.
4. **Premature trial termination by the sponsor, a regulatory agency, the IRB, or any other authority:** If the clinical trial is prematurely terminated by the sponsor, the investigator is to promptly inform the trial subjects and the local IRB and should assure appropriate follow up for the subjects. The primary reason for early termination in this case will be trial termination.
5. **Subject's death during trial participation.**
6. **Other** reason for early termination that is not captured by the above prespecified categories.

For screen failure subjects, refer to Section [9.1.11](#).

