2.1 Trial Design Diagram

2.2 Schedule of Trial Procedures

Day	Day 1	Day 8	Day 29	Day 85 ^(a)
Visit number	1	3	3	
Visit window		+2 days	+3 days	+ 14 days
Site visit	X	X	X	
Phone contact				X
Signed informed consent form	X			
Pregnancy test ^(b)	X			
Assessment of eligibility criteria ^(c)	X			
Demographics	X			
Medical history	X			
Prior medications	X			
Concomitant medications	X	X	X	X
Physical exam	Complete ^(d)	X		
	Symptom-directed		X	X
Vital signs ^(e)	X	X ^(d)	X ^(d)	
Vaccine administration	X			
30 min post-vaccination observation period	X			
Solicited AEs	X	X		
Unsolicited AEs	X	X	X	
Diary card provision ^(f)	X			
Diary card review ^(f)		X (Days 1–7)		
Serious adverse events ^(g)	X	X	X	X
AEs leading to withdrawal from trial	X	X	X	
Blood draw (max. 140 mL) ^(h)	X	X	X	

Notes on the next page.

Notes:

- (a) Day 85 corresponds to 84 days after trial vaccine administration at Day 1.
- (b) In women of childbearing potential, pregnancy tests (urine) will be performed on Day 1 before trial vaccine administration.
- (c) Assessment of eligibility criteria will be documented before trial vaccine administration.
- (d) Physical exam on Day 1 includes but is not limited to a check of general appearance, auscultation of heart and lungs, palpation of the abdomen, and inspection of extremities (including skin over the intended injection site), weight, and height. For any procedures at the site, the investigator shall follow his/her standard practice. If applicable, a symptom-directed physical examination (including vital signs) may be performed at the visits on Day 8 and Day 29.
- (e) Vital signs include but are not limited to heart rate and temperature.
- (f) Daily diary of solicited local and systemic adverse events (AEs) for 7 days following the trial vaccine administration.
- (g) Serious adverse events (SAEs) will be collected from the time the subject is administered the trial vaccine (Day 1) up to the end of the trial (Day 85).
- (h) The maximum volume of blood taken at any single site visit is approximately 30 to 140 mL, and the approximate total volume of blood taken during the trial is maximum 310 mL for all subjects. Samples will be taken for all subjects prior to trial vaccine administration on Day 1.

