10.4 Procedures

10.4.1 Collection and Reporting Procedures

All AEs, whether considered related to the use of the trial vaccine or not, must be monitored by the investigator until symptoms subside and any abnormal laboratory values have returned to baseline, or until there is a satisfactory explanation for the changes observed, or until death, in which case a full autopsy report should be supplied, if possible. All findings must be reported on the AE eCRF and on the paper SAE report form* if necessary (see Section 10.4.4). All findings in a subject experiencing an AE must also be documented in that subject’s source documents. Any unsolicited AE will be collected by the subject for 28 days post-dose. AEs leading to withdrawal from the trial are collected throughout the trial.

The following information will be documented for each event:

- Reported term for the AE.
- Start and end date, duration.
- Serious (Y/N).
- Intensity.
- Investigator’s opinion of the causality (relationship) between the event and administration of trial vaccine (related or not related).
- Investigator’s opinion of the causality (relationship) to trial procedure(s), including the details of the suspected procedure.
- Outcome of event.

*SAE reporting will be done with a paper SAE form emailed (encrypted) or faxed [REDACTED]:

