10.4.4 Collection and Reporting of Serious Adverse Events

Collection of SAEs will commence from the time that the subject is administered the trial vaccine (Day 1). Routine collection of SAEs will continue until the end of the trial (Day 85).

SAEs should be reported according to the following procedure:

A paper SAE report form must be completed, in English, and signed by the investigator immediately or within 24 hours of first onset or notification of the event. The information should be completed as fully as possible but contain, at a minimum:

- A short description of the event and the reason the event is categorized as serious.
- Causality assessment.
- Protocol number.
- Subject identification number.
- Investigator's name.

The paper SAE form must be transmitted within 24 hours to [REDACTED]

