10.5 Follow-up Procedures

10.5.1 Adverse Events

All AEs will be monitored until resolution or a stable status is reached, or until a formal diagnosis can be made or until the end of the trial, whichever occurs first.

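### Protocol 7.4 stops all data collection at early termination with no safety exception, contradicting the AE follow-up rules in 10.4.1 and 10.5.1: a small loss, cheap to repair

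*Protocol*

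**What the plan says.** Protocol 7.4 defines early termination of a subject's participation to mean that "no further trial procedures (including data collection) will be performed on that subject beyond the specific date of early termination of trial participation". The sentence precedes six reason categories and applies to all of them. None carries an exception for safety data.

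Item 1 (AE) has two limbs: staying in would put the subject's health at unacceptable risk, or "the subject is unwilling to continue participation because of the AE". In both, the reason is recorded as "withdrawal due to AE and not withdrawal of consent". Item 3 is withdrawal of consent, and item 6 is a residual category for other reasons.

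The safety sections set different limits:

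- **10.4.1:** every AE, related or not, "must be monitored by the investigator until symptoms subside", or until it is explained or the subject dies. It also says that "AEs leading to withdrawal from the trial are collected throughout the trial".
- **10.5.1:** AE follow-up ends at resolution, at a stable status, at a formal diagnosis, "or until the end of the trial, whichever occurs first".
- **10.4.4 and 2.2 note (g):** SAEs are collected from vaccination to the end of the trial, given as Day 85. The SAE endpoint in 5.2 also runs to the end of the trial.
- **9.1.8 and 13.1.4:** unsolicited AEs are collected through Day 28, counting the day of vaccination as Day 1.
- **10.5.4:** an SAE outside the observation period must still be reported if it is judged to be caused by the vaccine.

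**The concern.** By the time anyone can leave after vaccination, the full single dose has been given. What remains is two blood draws at most (30 mL on Day 8, 140 mL on Day 29), symptom-directed examinations and a phone call. There can be good reason to stop the draws for a subject who is unwell. That reason does not extend to a phone call asking how the AE turned out.

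Section 7.4 makes no such distinction. It ends safety data collection for the subjects whose safety course is of most interest, and it tells the investigator to do the opposite of what 10.4.1 and 10.5.1 require. At stake is the completeness of the secondary safety data: the course of the AE that ended participation, and later events up to Day 28 (unsolicited AEs) or Day 85 (SAEs).

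**Working it through.** The plan has no figure to reproduce on this point. The check compares the sections and then sizes the loss.

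**1. Which reasons for leaving are affected.** For loss to follow-up (item 2) and death (item 5) the rule changes little. For withdrawal of consent (item 3) stopping is expected. If the whole trial is terminated (item 4), the Day 85 schedule itself falls away, and 7.4 separately asks the investigator to see that subjects are followed appropriately. That leaves item 1 and item 6. Within item 1, the clear case is the unacceptable-risk limb, where the subject has not asked to leave.

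**2. Whether the instructions collide.** Take a subject terminated on Day 10 under that limb, with the AE still open.

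- 7.4: no data are collected after Day 10.
- 10.4.1 and 10.5.1: the AE is followed to resolution, stable status, diagnosis or the end of the trial. The subject's exit is not among the end points.
- 10.4.4 and 2.2 note (g): SAEs are collected to Day 85.

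The first two cannot both be followed. The third is in tension with 7.4 but could be read as the schedule for subjects still taking part.

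**3. What is kept and what is lost under a literal reading of 7.4.**

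- Kept: the AE that caused withdrawal (10.4.1, 10.4.2), with its outcome at exit, which 10.2.2 allows to be entered as not resolved or unknown; and later SAEs judged to be vaccine-caused (10.5.4).
- Lost: the later course of AEs open at exit, including any worsening; SAEs judged unrelated, up to Day 85; and new unsolicited AEs for anyone leaving before Day 28.

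Worsening matters for a planned table. Protocol 10.3 records an AE whose severity changes once, at its maximum intensity, and SAP 10.1.6 tabulates AEs leading to withdrawal by severity. If worsening after exit is not collected, the tabulated severity can be too low.

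**4. Size per subject.**

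- Leaves on Day 8: 85 − 8 = 77 days of SAE collection lost (77/85 = 90.6%), and 28 − 8 = 20 days of unsolicited AE collection lost (20/28 = 71.4%).
- Leaves on Day 29: 85 − 29 = 56 days of SAE collection lost (56/85 = 65.9%). The unsolicited AE window is already complete.

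**5. Size for the trial.** The documents give no withdrawal rate. Assume 0 to 2 of the 80 subjects leave under item 1 or 6 and can still be reached.

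- Subjects with truncated safety data: 0/80 to 2/80, that is 0% to 2.5%. The SAP counts subjects with events, so with 80 as denominator no incidence can shift by more than 2.5 percentage points.
- Planned person-days: 80 × 85 = 6,800. If both leave on Day 8, 2 × 77 / 6,800 = 2.26% is lost; if both leave on Day 29, 2 × 56 / 6,800 = 1.65%. The SAP does not analyse person-days, so these only show scale.

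The SAE figures are upper limits, because 10.5.4 still brings in vaccine-caused SAEs.

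**The case against.** The best defence is that 7.4 is the specific rule for subjects whose participation has ended, while the safety sections describe the general schedule. There is support for this. Section 10.4.4 speaks of routine collection, and 10.5.2 asks for SAE follow-up within the trial. This softens the conflict on SAEs, and a reader who infers a flat contradiction with 10.4.4 and note (g) goes further than the text allows. It does not settle the conflict on AEs: 10.4.1 and 10.5.1 cover all AEs, and no section says that 7.4 overrides them. Even if it did, the follow-up would still be lost.

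A reader might also infer that the AE causing withdrawal goes unrecorded, or that every SAE after exit is missed. Neither follows. The withdrawal AE is recorded under 10.4.1 and 10.4.2, and 10.5.4 on its face covers vaccine-caused SAEs after exit. That clause does make capture depend on the causality judgement, a limit that the SAE endpoint in 5.2 does not have.

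Three further objections hold in part. No SAP table uses AE outcome, so a missing final outcome by itself changes no planned tabulation; missed worsening, unrelated SAEs and new unsolicited AEs can. A subject who leaves because unwilling to continue is close to withdrawing consent, so stopping there is defensible and contact needs the subject's agreement. And the number affected is assumed, not known.

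**Conclusion.** The point holds as a limited one. Section 7.4 contradicts 10.4.1 and 10.5.1 for subjects terminated because of an AE, chiefly under the unacceptable-risk limb of item 1, or for another reason without withdrawal of consent. It is in tension with SAE collection to Day 85, but not plainly contrary to it.

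The loss is large for an affected subject and probably very small for the trial: at most 2.5% of subjects if no more than 2 of 80 are affected, which is an assumption. How many SAEs would be missed cannot be estimated from the documents.

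It would be wrong to infer that the primary objective is weakened. The immunogenicity analysis and the serum-based sample size do not depend on safety follow-up after exit, and stopping blood draws is not disputed. Priority is low.

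**What to change.** Add a clause to Protocol 7.4 along these lines:

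- Unless the subject withdraws consent to further contact, blood draws and other procedures stop at early termination, but safety follow-up continues.
- AEs open at termination are followed to the end points in 10.5.1.
- Unsolicited AEs are collected to Day 28. A short call around Day 29 can replace the interview planned in 9.3.4.
- SAEs are collected to Day 85 through the phone call already planned in 9.3.5.
- Subjects who leave because they are unwilling to continue, or who withdraw consent, are contacted only if they agree. Section 9.1.10 already makes pregnancy follow-up conditional on agreement in this way.

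The cost is a short amendment with IRB handling (15.1), a few phone calls and, if the consent form describes what happens on leaving, revised wording and re-signing (15.2). The consent form was not available for this review, so it may already allow such contact.
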